## **DATA HANDLING**

### **Personal Data Protection**

All data collection material will be de-identified. Participant records will be distinguished using participant identification (PID) numbers.

### **DATA RETENTION**

Records and documents pertaining to the conduct of the study as well as all data collected as part of the study will be retained in a secure place for 25 years in accordance with Health Canada regulations. All data collected throughout the study will be kept with membership of the BCDF for 25 years.

## **PARTICIPANT PROTECTION**

Participants will not be placed at any risk as a result of the study. Information obtained will be maintained in a secure and confidential fashion. No participant will be coerced and/or placed under duress to complete study procedures.

## **PARTICIPANT COMPENSATION**

All participants (i.e., patients with DSM-5-defined MDD and healthy controls) will be provided with reasonable compensation (i.e., \$150 CAD, plus modest out-of-pocket expenses for parking/public transit and food per visit maximum \$30 CAD per visit) following successful completion of the clinical trial in its entirety. A cheque will be provided as reimbursement for every visit up to \$30. Healthy participants will be reimbursed \$100 CAD, plus up to \$30 CAD for travel and food.

## **ADVERSE EVENTS**

An adverse event (AE) is the development of an undesirable medical condition or the deterioration of a pre-existing medical condition following or during exposure to a pharmaceutical product, whether or not considered causally related to the product. An undesirable medical condition can be symptoms (e.g., nausea, chest pain), signs (e.g., tachycardia, enlarged liver) or the abnormal results of an investigation (e.g., laboratory findings, electrocardiogram). In clinical studies, an AE can include an undesirable medical condition occurring at any time, including run-in or washout periods, even if no study treatment has been administered.

### **Serious adverse events**

A serious adverse event (SAE) is an AE occurring during any study phase (i.e., run-in, treatment, washout, follow-up), and at any procedure, that fulfills one or more of the following criteria:

- Results in death
- Is immediately life-threatening
- Requires inpatient hospitalization or prolongation of existing hospitalization

- Results in persistent or significant disability or incapability
- Is a congenital abnormality or birth defect
- Is an important medical event that may jeopardize the patient or may require medical intervention to prevent one of the outcomes listed above

The causality of SAEs (i.e., their relationship to study treatment) will be assessed by the investigator(s). Note that SAEs that could be associated with any study procedure should also be reported. For such events the causal relationship is implied as “yes”.

## Recordings of Adverse Events

Adverse events will be collected from baseline to endpoint. At each visit, subjects will be asked if they have experienced any health problems or side effects since the previous visit. All AEs will be recorded appropriately, whether or not considered related to the investigational product. This will include AEs spontaneously reported by the patient and/or observed by members of the research team as well as AEs reported in response to a direct question (e.g., “Have you experienced any health problems of side-effects since your last visit?”).

For each AE, the following parameters will be described:

- Start and Stop date
- Action taken with regards to investigational product
- Outcome
- If the AE caused the patient to discontinue the investigational product
- A statement if the AE fulfills the criteria for a SAE or not
- The investigator’s assessment of the causal relationship between the event and the investigational product
- Intensity of the AE
  - o Mild (awareness of sign or symptom, but easily tolerated)

- o Moderate (discomfort sufficient to cause interference with normal activities)
- o Severe (incapacitating, with inability to perform normal activities)

It is important to distinguish between serious and severe AEs. Severity is a measure of intensity. An AE of severe intensity need not necessarily be considered serious. For example, nausea that persists for several hours may be considered severe nausea, but not an SAE. On the other hand, a stroke that results in only a limited degree of disability may be considered a mild stroke but would be an SAE. Symptoms associated with overdose will be reported as AEs. Pregnancy in itself is not regarded as an AE. Follow-up of adverse events will be based upon the clinical judgment of the investigator.

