## **Transition to Enrollment**

Patient will discontinue only antidepressants. Patients' existing antidepressant dosage will be decreased gradually over a course 10-14 days. At the same time, participants will be started on 10mg of Vortioxetine. It takes about 10-14 days for Vortioxetine to achieve steady states. For patients who are already taking antidepressants at the start of study, if they are abruptly discontinued, they are at risk for discontinuation syndrome. Therefore, both drugs will be co-prescribed for about 10-14 days and then the index antidepressant will be discontinued.

Serotonin syndrome or other additive side effects is very unlikely to be a concern. Should the patient's physician determine another optimal schedule, this will be followed instead. All MDD participants will be supervised by [name], prior to enrollment of the study. All patients will be monitored by a psychiatrist during the study. Furthermore, patients will have access to a 24-hour study number where they can contact research staff anytime, should they experience any adverse events. Therefore, there will always be an open line of communication between patients and the research staff.

The above mentioned procedures will only be carried out once participants have consented to take part in the research and signed the informed consent form.

Patients will be seen by a clinician on a biweekly basis for the antidepressant washout period. Clinician will be assessing the patient on adverse side effects, as well as mood.

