### ***Post Visits – Transition to Standard of Care***

Upon completion of the study, patient will be seen by research team clinician to determine whether medication will be discontinued. If medication discontinuation is required, the patient will receive medication reduction by clinician for a period of one week, followed by a period of 1 week with no medication. Patient will be seen by physician 2 weeks post week 8, to monitor well being, including mood, adverse events and any suicide risks. This is a clinical visit with the psychiatrist and will undergo a full clinical psychiatric assessment to assure patient has a smooth

transition to standard of care with their main responsible physician. Should the patient need to see physician sooner, they are advised to contact the 24/7 study line to schedule an appointment. MDD participants will be followed up by physician but will not undergo ongoing provision of care after the study by the research physician.

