### **MDD PATIENT SUMMARY CHART**

Visit	Screening (Visit 1)	Week 0 (Baseline, Visit 2)	Week 2 (Visit 3)	Week 4 (Visit 4)	Week 8 (Endpoint, Visit 5)	Post-Study two weeks clinical visit for drug discontinuation. Additional visits will be scheduled as needed.
Consent	X					
Physician visit		X	X	X	X	X
Bloodwork		X			X	
Demographics	X					
Inclusion/ exclusion	X					
Adverse events	X	X	X	X	X	
Current Medications	X					
Medication Changes		X	X	X	X	
M.I.N.I 5.0	X					
SCID	X					
Psychiatric/Medical History	X					
Anthropometrics	X	X	X	X	X	
Lifestyle Factors	X	X	X	X	X	
Montgomery Åsberg Depression Rating Scale (MADRS) > 20	X	X	X	X	X	
THINC-it Practice		X				
THINC-it Cognitive test		X	X		X	
CSSRS	X	X	X	X	X	
DSST (pen/paper)		X	X		X	
TMT-B (pen/paper)		X	X		X	
NART	X					
CGI-I/CGI-S		X	X	X	X	
International Physical Activity Questionnaire (IPAQ)		X		X	X	
Vortioxetine Treatment		X	X	X		
Dispensing medication		X	X	X		
Effort Expenditure for Rewards Task (EEfRT) – optional					X	

Endicott Workplace Productivity Scale (EWPS)		X	X		X	
Sheehan Disability Scale (SDS)		X	X		X	
Wellbeing Index (WHO-5)		X	X		X	
Snaith-Hamilton Pleasure Scale Questionnaire (SHAPS)		X	X		X	
Generalized Anxiety Disorder (GAD-7)		X	X		X	
Perceived Deficits Questionnaire for Depression (PDQ-5-D)		X	X		X	
36-Item Short Form Survey Instrument (SF-36)		X	X		X	
Insomnia Severity Index (ISI)		X	X		X	
Pittsburgh Sleep Quality Index (PSQI)		X	X		X	
Epworth Sleepiness Scale (ESS)		X	X		X	
THINC-it satisfaction questionnaire		X				

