## **Transition to Standard of Care**

Patients will be informed of the transition to standard of care procedures (outlined here) post study prior to providing consent to participate in the study. These procedures will also be outlined in writing in the patient consent form itself.

Upon completing the 8-week course of vortioxetine, if patients benefit from this drug, they will be encouraged to continue the treatment with their most responsible physician (MRP). Patients will be notified prior to study consent that not all drug plans will cover the cost of vortioxetine. Should patients wish to continue to use this drug post-study when they do not have coverage, they will be personally responsible for the costs. There will be a gradual discontinuation of the medication for two weeks after the end of the study. However, participants will not have further access to this drug from the research team after study completion. If patients do experience side effects during the study, a physician will make a recommendation regarding the discontinuation or dose reduction of the medication for the remainder of the study. If patients do not experience

any improvement upon study completion in mood or cognition, the medication will be gradually discontinued over a two-week period upon study completion (week 8).

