## **Vortioxetine discontinuation process**

At visit 8, patients will be seen by a clinician and provided with half of current vortioxetine dosage for a period of 1 week. This down titration will assure there are no adverse side effects with discontinuation of vortioxetine. During the second week, patients will not be on medication and will be seen by the clinician at the end of two weeks, to ensure that there are no risks or adverse events during this time period. The visits with the clinician are post-study, and not part of the study visits. Patients are encouraged to contact the 24/7 study phone line in the event that they would like to be scheduled with the physician earlier. MDD patients will be seen by research clinician to ensure a safe transition into standard of care by their main responsible physician.

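### Adverse event collection stops at Week 8, so new non-serious events in the two weeks of vortioxetine taper and withdrawal do not enter the trial data, although a physician already asks about them

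*Combined protocol and SAP*

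**What the plan says.** **Collection window.** Recordings of Adverse Events sets the rule: "Adverse events will be collected from baseline to endpoint". The MDD Patient Summary Chart gives Week 8 (Visit 5) as the endpoint. Its adverse events row is marked at screening and Weeks 0, 2, 4 and 8. It is blank in the last column, headed "Post-Study two weeks clinical visit for drug discontinuation", although the physician visit row is marked there.

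**What happens after Week 8.** Vortioxetine discontinuation process says that patients are "provided with half of current vortioxetine dosage for a period of 1 week", followed by a week without medication and a clinician contact at the end of it. It places the start at visit 8. The chart has only five visits, so I read this as Week 8. Post Visits – Transition to Standard of Care gives the same one-week-plus-one-week schedule and adds: "Patient will be seen by physician 2 weeks post week 8, to monitor well being, including mood, adverse events and any suicide risks".

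**Status of that contact.** Vortioxetine discontinuation process states: "The visits with the clinician are post-study, and not part of the study visits".

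**Consent.** Transition to Standard of Care says of the post-study arrangements: "These procedures will also be outlined in writing in the patient consent form itself".

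**The concern.** The window closes while some patients are about to take a reduced dose of study drug supplied by the study clinician and then come off it. The plan treats this period as clinically relevant: it tapers the dose to avoid discontinuation effects and arranges for a physician to ask about adverse events when it ends. Nothing in the plan says that a new, non-serious event reported at that contact is written into the trial record.

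What is at stake is how complete the safety record is. For a patient who stops, it would hold no new non-serious events from the last days on drug or the first days off it, although someone on the research team will have asked. Patient care does not depend on this, nor do the primary and secondary objectives or the THINC-it comparison.

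**Working it through.** No sample size, power or error-rate figure bears on this point, and the plan gives no figure of its own to reproduce. The check sets the collection window against the exposure and withdrawal period, in days, for a patient who stops at Week 8.

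**Inputs**

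- Collection window: Day 0 to Day 56 (Recordings of Adverse Events; Week 8 as endpoint in the MDD Patient Summary Chart).
- Half-dose period: 7 days after Day 56 (Post Visits – Transition to Standard of Care; Vortioxetine discontinuation process).
- Drug-free period: the next 7 days (same two sections).
- Post-study physician contact: two weeks after Week 8, so Day 56 + 14 = Day 70.

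**Arithmetic**

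- Days outside collection: 7 + 7 = 14.
- Share of the time from first dose to the post-study contact: 14 / (56 + 14) = 14/70 = 20.0%.
- Share of dosing days outside collection: 7 / (56 + 7) = 7/63 = 11.1%, all at half dose.
- With recording extended to the existing contact, the window runs from Day 0 to Day 70 and no day is left out.

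**Does any other text already close the gap?**

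| Text | What it does | Closes the gap? |
|---|---|---|
| Adverse Events: the definition allows for events in washout | Defines what counts as an event | No; it sets no collection period |
| Serious adverse events: the definition spans all study phases, including washout and follow-up | Defines serious events | Not for non-serious events |
| Reporting of Adverse and Serious Adverse Events: follow national rules | Covers events that must be reported | Only for those events |
| Recordings of Adverse Events: ask at each visit | Applies to visits | No; the taper contacts are declared not to be study visits |
| Recordings of Adverse Events: follow-up by investigator judgment | Most naturally concerns events already identified | No provision for new ones |
| 24-hour study line and physician contact | Clinical oversight | Not linked to trial recording |

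The rule, the chart and the stated status of the visit all agree, so the blank cell is not an accident of a broken table.

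**The case against.** The strongest reply is that this boundary is coherent and chosen. Three places in the protocol agree on it, no objective concerns safety, and the Statistical Plan contains no adverse event analysis, rate or safety population. Serious events, reportable reactions and clinical care are dealt with elsewhere. What remains is new, non-serious, non-reportable events in the subset of patients who stop. All of that stands, and it is why the point is minor. It does not answer why the response to a question already being asked should be left out of the record.

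Four stronger readings are tempting, and the documents do not support them.

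- **A contradiction with the event definitions.** A reader might infer that the definitions, which mention washout, conflict with the window. They are definitions only. The protocol's own use of the term concerns the earlier switch from a previous antidepressant: "Patients will be seen by a clinician on a biweekly basis for the antidepressant washout period". Vortioxetine starts at the same time as that switch, so it falls inside the window.
- **Fourteen on-drug days missed.** Transition to Standard of Care says that, for patients without improvement, "the medication will be gradually discontinued over a two-week period upon study completion (week 8"). Taken alone, this could put 14 of 70 on-drug days (20.0%) outside collection. The two sections that set out the schedule in detail give one week at half dose and one week off drug, and the two-week wording reads naturally as a summary of that. The supported figure is 7 on-drug days.
- **A fifth of adverse events lost.** A share of days does not measure events. The protocol gives neither the number of patients who stop nor an event rate for these weeks. For gastrointestinal events, listed among the most common, the Side effects section puts the highest incidence in the first week of treatment, which is inside the window.
- **Patients left unmonitored.** They are not: there is a physician contact, a taper and a 24-hour line.

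A further objection concerns the remedy. If collection were extended only for patients who stop, observation time would depend on treatment outcome, because patients without improvement are tapered while those who benefit are encouraged to continue with their own physician. That objection is sound, and the fix below allows for it.

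It is also true that the window is not strict at its start, since events are recorded at screening, before baseline. At its end, however, rule and chart agree.

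**Conclusion.** The point holds as a low-cost improvement to the safety record. New non-serious events in the 14 days after Week 8 (7 on half dose, 7 off drug) are excluded from trial data by the collection rule, although a physician contact that asks about adverse events is already scheduled at the end of that period. I attach no count of missed events, because the documents supply no basis for one.

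This rests on three assumptions: that visit 8 in the discontinuation section means Week 8; that the one-week-plus-one-week schedule in the two detailed sections governs; and that the consent form and case report forms, which are not in the documents, do not already provide for this recording. Patients who continue vortioxetine with their own physician do not go through the taper, so the 14-day figure applies only to those who stop. It concerns stopping at Week 8, not withdrawal before it. The Week 8 THINC-it results and the stated objectives do not change.

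**What to change.** 1. In Recordings of Adverse Events, extend recording of adverse and serious adverse events to the existing contact two weeks after Week 8, for every MDD patient who attends it and not only for those who stop.
2. In the MDD Patient Summary Chart, mark the adverse events row in the post-study column.
3. In Vortioxetine discontinuation process, state that events found at that contact are recorded with the same parameters as during the study, and flag each one as on taper, off drug, or continuing with own physician.
4. Summarise these events separately from those of Weeks 0 to 8. Attendance and drug status after Week 8 may depend on treatment outcome, so pooling the two periods would mix unequal observation times.

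Week 8 stays as the endpoint for THINC-it and all other outcomes.

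**Cost.** Slight extra recording at a contact that already takes place, and a matching line in the consent form, because the contact is now described as outside the study. No new visit is needed, and neither the sample size nor the primary analysis changes.

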## **Reporting of Adverse and Serious Adverse Events**

The sponsor-investigator will comply with any and all national rules and regulations concerning safety reporting (adverse drug reactions or SAEs as required). All SAEs (according to the definition in ICH GCP) will be will be done by the investigator in accordance with local regulations and reported to the appropriate regulatory bodies.

